Exploring the role of tryptophan metabolites in pediatric migraine

2023.05.01

1. Research objectives, study content and key questions to be addressed

1.1 Research objectives This research focuses on the key scientific issues of "tryptophan metabolites and childhood migraine", and explores the pathogenesis, diagnosis, treatment, and prevention of childhood migraine by combining clinical characteristics and medical history and other multi-level data, with the aim of establishing an assessment system for early identification and intervention of childhood migraine, systematically developing an individualized treatment and assessment system for childhood migraine, and conducting clinical translational research in the field of childhood migraine. We aim to establish an assessment system for early identification and intervention of childhood migraine, systematically carry out individualized treatment and assessment system for childhood migraine, and conduct clinical translational research in the field of childhood migraine. The following are the details: The aim of the study is to establish a system for the early identification and intervention of migraine in children, and to systematically develop an individualized treatment and evaluation system for migraine in children.

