2.1 Experimental protocol

2.1.1 Inclusion and exclusion criteria of study subjects

Case group inclusion criteria:(1) Age 4-18 years old, male and female are not limited. (2) Meet the diagnostic criteria of ICHD-3 with aura, without aura, and chronic migraine. (3) Migraine was diagnosed by two or more specialized neurologists. (4) PedMIDAS score > 11 (5) Migraine had never been treated (6) Patients and families gave informed consent to the study purpose, significance, risks, benefits, and informed consent. Source: Department of Pediatrics Outpatient and Inpatient Unit, Oilu Hospital. Shandong University

Inclusion criteria for the control group:(1) Age 6-18 years, male and female. (2) Did not meet the diagnostic criteria of ICHD-3 migraine and other headaches. (3) Physical health allowed their participation in the study. (4) Patients and their families gave informed consent to the study purpose, significance, risks, benefits, and information of the study. Source: Department of Pediatrics Outpatient and Inpatient Unit, Oilu Hospital. Shandong University.

Exclusion criteria:

(1) presence of drug overdose (2) autoimmune diseases (3) neurological diseases other than migraine, intracranial masses (4) congenital or hereditary diseases (5) diabetes, bronchial asthma, cardiovascular diseases, pulmonary diseases (6) other types of primary and secondary headache.

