2.1.2 Data collection

(1) Data sources: questionnaires, outpatient medical records and auxiliary examination results.

(2) Collection methods: questionnaire survey, medical records review, blood collection.

(3) Data composition: Basic personal information, migraine triggering factors, clinical features of headache, medication, past medical history, ancillary examinations, and blood samples were collected from all enrolled headache patients.

① Basic personal information included name, gender, age, height, weight (calculated BMI) cultural level, residence address, and contact information.

② Migraine triggering factors: genetic factors, endocrine (menstruation), diet (cheese, chocolate, puffed food), psychological factors (sleep, anxiety, depression, emotional stress, etc).

③ Clinical characteristics of headache included: whether the patient was in the attack phase or inter-attack phase, the location of the patient's headache, the nature of the headache, the degree of pain (assessed using the visual analog scale VAS Appendix), the duration of the disease (years), the frequency of the headache, the duration of each headache, the time of the last pain, the presence of aura, aura symptoms, concomitant symptoms (photophobia, phonophobia, nausea, vomiting, gastrointestinal

symptoms),exacerbation and remission. The information of each headache, duration of last pain,presence of aura, aura symptoms, concomitant symptoms (photophobia, photophobia.nausca, vomiting, gastrointestinal symptoms), aggravation and relief factors, familyhistory, etc.

④Also record medication use, past medical history, ancillary test results such asroutine blood, liver function, kidney function, lipids, blood glucose, ECG, TCD, headCT,head MRIhead MRA examination,etc.PedMIDAS scale score, migraine treatment efficacy assessment scale, headachediary

⑤5ml of venous blood

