2.1.4 Data analysis

Statistical analysis was performed using SPSS26.0 software analysis, and statisticaldata were tested for normality, and the mean standard deviation ($x + S$) was used formeasurement data that conformed to the normal distribution, and one-way ANOVAwas applied for comparison between the three groups, and t-test for two independentsamples was used for comparison between two groups. The correlation between theplasma levels between migraine attacks and the duration of the disease was analyzedby SPSS26.0 correlation analysis.

(1) After completing the questionnaire survey, the researchers collected data

and analyzed the risk of migraine in children due to the interaction of multiple factors, and used logistic regression to screen the indicators related to the risk of migraine in children due to the interaction of multiple factors, and established an early assessment model of migraine in children to achieve early detection, early diagnosis and early prevention of migraine in children.

(2) Based on the collected medical history, different group analyses were performed, and the plasma levels of tryptophan metabolites in migraine patients were compared with those in healthy controls by t-test; one-way ANOVA was performed on the plasma levels of tryptophan metabolites between different types of migraine; correlation analyses were performed between the frequency, duration, severity and two types of migraine attacks; and logistic regression was performed to screen for possible influences on the risk of migraine in children. Logistic regression was performed to screen the factors that may influence the diagnosis of migraine in children.

(3) To analyze the diagnostic value of tryptophan metabolite and tryptophan metabolite combined diagnosis by ROC curve, and to analyze whether there is any statistical difference between the three diagnostic indexes by independent sample t-test, and to evaluate the diagnostic indexes of tryptophan metabolite and tryptophan metabolite combined diagnosis by diagnostic test, and to evaluate the diagnostic indexes of tryptophan metabolite and tryptophan metabolite combined diagnosis as the possibility and accuracy of specific diagnostic indexes for migraine in children were evaluated.

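### The logistic screen in 2.1.4(1) is presented as being about migraine, but cases are limited to PedMIDAS > 11, so its odds ratios mix association with migraine and association with disability

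*SAP*

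**What the plan says.** Section 2.1.1 requires cases to meet ICHD-3 migraine criteria and, as item (4), to have "PedMIDAS score > 11". Controls enter under "Did not meet the diagnostic criteria of ICHD-3 migraine and other headaches".

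Section 2.1.4(1) states that the researchers "used logistic regression to screen the indicators related to the risk of migraine in children", and that they "established an early assessment model of migraine in children to achieve early detection, early diagnosis and early prevention of migraine in children". The aims in section 1.1 are equally general: to "establish a system for the early identification and intervention of migraine in children".

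Among the items collected, section 2.1.2 lists "psychological factors (sleep, anxiety, depression, emotional stress, etc" under triggering factors. PedMIDAS appears again there, but only as a recorded score. The SAP does not restrict the logistic conclusions to children above the cut-off, give a reason for the cut-off in this analysis, or plan a sensitivity analysis for it.

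**The concern.** The outcome analysed and the outcome claimed differ. The regression compares children who have migraine and score above 11 with children who have no headache disorder. The text reads the result as being about migraine.

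Some candidate factors, such as poor sleep, anxiety, depression and stress, could plausibly raise disability in a child who already has migraine without altering whether the child has it. Children with such a factor would pass the PedMIDAS criterion more often and be over-represented among cases. Controls face no such criterion. Part of the odds ratio would then reflect what separates more disabling from milder migraine.

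At stake is the label on the screened factors and the use of the model. A tool meant for early detection and prevention would be built without the lower-scoring children, who are natural targets for early detection. Covariate adjustment, internal validation or a larger sample cannot repair this, because those children are not enrolled.

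**Working it through.** The SAP states no sample size, power, effect size or share of migraine above the cut-off, so there is no figure of its own to reproduce. The case and control definitions come from 2.1.1 and the target of inference from 2.1.4(1). All numerical inputs below are assumptions.

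**Step 1: the selection factor.** Let q1 and q0 be P(PedMIDAS > 11 | migraine) with and without a factor. Let the factor have prevalence m among all children with migraine and p among controls. After the cut-off, the odds of the factor in cases are m·q1 / [(1 − m)·q0]. Dividing by the control odds p/(1 − p) gives

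observed OR = OR for migraine × q1/q0.

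This isolates the PedMIDAS criterion, with no other selection acting. If the factor is unrelated to the score, q1 = q0 and nothing changes. Because q1 cannot exceed 1, the multiplier cannot exceed 1/q0.

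**Step 2: a range.** Let d be the odds ratio linking the factor to PedMIDAS > 11 among children with migraine. Then q1 = d·q0/(1 − q0 + d·q0), so q1/q0 = d/(1 − q0 + d·q0). For a factor with no relation to having migraine (true OR 1), the observed OR is:

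| q0 | d = 1.5 | d = 2 | d = 3 | cap 1/q0 |
|---|---|---|---|---|
| 0.3 | 1.30 | 1.54 | 1.88 | 3.33 |
| 0.5 | 1.20 | 1.33 | 1.50 | 2.00 |
| 0.7 | 1.11 | 1.18 | 1.25 | 1.43 |
| 0.9 | 1.03 | 1.05 | 1.07 | 1.11 |

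Example: q0 = 0.5 and d = 2 give 2/(0.5 + 1.0) = 1.33, with q1 = 0.667. If 30% of controls have the factor, its prevalence in enrolled cases is 0.3 × 0.667 / (0.3 × 0.667 + 0.7 × 0.5) = 0.200/0.550 = 36.4%.

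**Step 3: chance of a nominally significant result.** This uses an unadjusted comparison of two proportions, two-sided 5%, equal groups and control prevalence 30%. Only results in the upward direction are counted, for which the chance would be 2.5% without bias.

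| Assumption | Observed OR | 50 per group | 100 per group | 200 per group |
|---|---|---|---|---|
| q0 = 0.9, d = 1.5 | 1.03 | 3% | 3% | 4% |
| q0 = 0.5, d = 2 | 1.33 | 10% | 16% | 27% |
| q0 = 0.3, d = 3 | 1.88 | 32% | 57% | 86% |

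**Step 4: the opposite error.** A factor with a true OR of 0.75 for migraine and q1/q0 = 1.33 would show 0.75 × 1.33 = 1.00. The restriction can hide an association as well as create one.

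**The case against.** A reader might infer that any factor which worsens disability will be reported as a migraine risk factor. The SAP does not support that. The multiplier depends on q0 and on the strength of the link with disability, and neither is given. If most children seen at this hospital score above 11, the distortion is close to nil. Whether a factor is reported also depends on a sample size and a selection rule that are not stated, and on the factor's true relation to migraine.

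Four further objections have weight.

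- **Control data.** Section 2.1.2 describes collecting these items from headache patients, and for recruited children generally 2.1.3 mentions only basic information and headache characteristics. As written, a case-control odds ratio for sleep or anxiety may not be computable. This stands: the point applies only to factors also measured in controls.
- **Other selection.** Cases must also be untreated, and both groups come from the hospital's outpatient and inpatient units. If more disabled children are treated more often, the first works in the opposite direction; hospital controls may themselves have more sleep or emotional problems. The net direction is therefore not established.
- **Case definition.** A disability threshold is an ordinary case definition, and the aims in 1.1 include intervention and individualized treatment. For migraine above the cut-off versus no headache, the criterion introduces no bias. This also stands, and it is why the remedy is one of labelling.
- **Cost of wider enrolment.** Admitting lower-scoring children to one analysis would mean recruiting and consenting more children and would create two case populations.

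None of this removes the mismatch: the SAP claims migraine in general and enrols only part of it.

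**Conclusion.** The concern holds as a mismatch between the enrolled case definition and the stated inference. That mismatch is plain from 2.1.1 and 2.1.4(1) and needs no outside figure. Its numerical effect is unknown: the multiplier is q1/q0, capped at 1/q0, and the assumed ranges give spurious odds ratios from about 1.03, which is negligible, to 1.88, which is not. These figures treat the PedMIDAS criterion as the only selection acting and assume the factor was recorded in controls. Other selection could add to the effect or offset it. The supportable conclusion is that factors linked to disability can be misread as risk factors for migraine, not that they will be.

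**What to change.** In 2.1.4(1), define the outcome as migraine with PedMIDAS > 11 versus no headache. Limit the early assessment model's stated use and conclusions to that population. State that factors which may affect disability (sleep, anxiety, depression, stress) will not be interpreted as risk factors for migraine onset. For consistency, carry the same label to the logistic regression in 2.1.4(2), which is also worded in terms of migraine risk.

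This is a change of wording and needs no new data. The cost is a narrower stated conclusion. Enrolling lower-scoring children for the questionnaire analysis would allow a broader claim, but it is optional and outside this fix: it means extra recruitment and consent and a second case population, and it would leave the untreated and hospital-based selection in place.

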2.1.2 Data collection

(1) Data sources: questionnaires, outpatient medical records and auxiliary examination results.

(2) Collection methods: questionnaire survey, medical records review, blood collection.

(3) Data composition: Basic personal information, migraine triggering factors, clinical features of headache, medication, past medical history, ancillary examinations, and blood samples were collected from all enrolled headache patients.

① Basic personal information included name, gender, age, height, weight (calculated BMI) cultural level, residence address, and contact information.

② Migraine triggering factors: genetic factors, endocrine (menstruation), diet (cheese, chocolate, puffed food), psychological factors (sleep, anxiety, depression, emotional stress, etc).

③ Clinical characteristics of headache included: whether the patient was in the attack phase or inter-attack phase, the location of the patient's headache, the nature of the headache, the degree of pain (assessed using the visual analog scale VAS Appendix), the duration of the disease (years), the frequency of the headache, the duration of each headache, the time of the last pain, the presence of aura, aura symptoms, concomitant symptoms (photophobia, phonophobia, nausea, vomiting, gastrointestinal

symptoms),exacerbation and remission. The information of each headache, duration of last pain,presence of aura, aura symptoms, concomitant symptoms (photophobia, photophobia.nausca, vomiting, gastrointestinal symptoms), aggravation and relief factors, familyhistory, etc.

④Also record medication use, past medical history, ancillary test results such asroutine blood, liver function, kidney function, lipids, blood glucose, ECG, TCD, headCT,head MRIhead MRA examination,etc.PedMIDAS scale score, migraine treatment efficacy assessment scale, headachediary

⑤5ml of venous blood

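### The severity correlation pools one VAS score over cases aged 4 to 18 with no age term, although age is collected, so it could reflect age in place of pain

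*SAP*

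**What the plan says.** - **Who is measured.** The case-group criteria in SAP 2.1.1 read "Age 4-18 years old, male and female are not limited". Controls are 6-18 years, but they have no migraine severity and do not enter this analysis.
- **How pain is measured.** SAP 2.1.2, item 3, lists "the degree of pain (assessed using the visual analog scale VAS Appendix" among the headache characteristics. The text names no other measure of pain intensity and no variant of the scale by age. The appendix is not shown.
- **What else is recorded.** SAP 2.1.2, item 4, adds "PedMIDAS scale score, migraine treatment efficacy assessment scale, headachediary". PedMIDAS is also an entry criterion: "PedMIDAS score > 11" (2.1.1).
- **How severity is analysed.** SAP 2.1.4(2) states that "correlation analyses were performed between the frequency, duration, severity and two types of migraine attacks", and 1.2.1 says nearly the same. Neither place names the coefficient, the variable that stands for severity, or any adjustment. The metabolite is not named as the other variable in that clause, though the preceding clauses concern plasma metabolite levels.
- **Whether age is available.** It is: "Basic personal information included name, gender, age, height, weight (calculated BMI" (2.1.2, item 1).

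**The concern.** A span of 4 to 18 years covers large developmental change. A self-reported pain score may shift with age because children of different ages use a scale differently, and metabolite levels may also change with age. If both happen, a correlation pooled over all ages mixes the link of interest (pain with metabolite) with two others (age with score, age with metabolite). It can then show an association where pain and metabolite are unrelated at any given age, or hide one that exists.

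A second mechanism is measurement error. If the youngest children's scores are noisier, a true association is pulled towards zero.

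The severity correlation is one of the analyses that SAP 1.2.1 combines to explore the pathogenesis of childhood migraine. A coefficient driven by age would be read there as evidence about pain.

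**Working it through.** The SAP gives no sample size, effect size, reliability or age mix, so there is no figure of the plan's own to reproduce. Everything below is illustrative.

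**1. Age in place of pain (true correlation 0)**

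Assumed inputs: a share p of young cases, 0.15 to 0.40; VAS mean 1 SD higher and metabolite mean 0.5 SD higher in the young; unit variance and zero correlation within each age group.

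- Pooled covariance = 1 × 0.5 × p(1−p)
- Pooled variances: VAS 1 + p(1−p); metabolite 1 + 0.25p(1−p)
- Pooled r = 0.5p(1−p) / √{[1 + p(1−p)][1 + 0.25p(1−p)]}

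p = 0.15: p(1−p) = 0.1275, so r = 0.0638 / √(1.1275 × 1.0319) = 0.059.
p = 0.40: p(1−p) = 0.24, so r = 0.12 / √(1.24 × 1.06) = 0.105.

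False-positive rate at two-sided 0.05 by Fisher z, with an assumed n = 100: let d = atanh(r) × √97; the rate is 1 − Φ(1.96 − d) + Φ(−1.96 − d).

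- r = 0.059: d = 0.583, rate 9.0%
- r = 0.105: d = 1.035, rate 17.9%

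**2. Does adjustment remove it?**

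At p = 0.40 the correlation of age group with VAS is √(0.24/1.24) = 0.440, and with metabolite √(0.06/1.06) = 0.238. Their product is 0.105, the whole of the pooled r. The numerator of the partial correlation, r minus that product, is therefore 0.

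**3. Dilution (assumed true r 0.30)**

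Assumed reliability is 0.8 in older children and 0.2 or 0.5 in the young. Older children alone give 0.30 × √0.8 = 0.268. The pooled value depends on the error model:

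- Equal VAS variance in both groups: r = 0.30 × [p√rel(young) + (1−p)√0.8]
- Additive error: r = 0.30 / √[1 + p(1−rel)/rel + (1−p) × 0.25], where rel is reliability in the young

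| Share young | Reliability in young | Pooled r, equal variance | Pooled r, additive error |
|---|---|---|---|
| 15% | 0.5 | 0.260 | 0.257 |
| 15% | 0.2 | 0.248 | 0.223 |
| 40% | 0.5 | 0.246 | 0.241 |
| 40% | 0.2 | 0.215 | 0.181 |

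The loss against 0.268 runs from 3% (0.260) to 33% (0.181). With milder assumptions (5% young, reliability 0.6 in the young and 0.9 in the older), the additive model gives 0.281 against 0.285, a loss of about 1%.

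**4. Would restricting to older children be better?**

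Power by Fisher z, with an assumed 100 cases in total, so 85 or 60 older children:

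| Share young | Reliability in young | Pooled, equal variance | Pooled, additive error | Older only |
|---|---|---|---|---|
| 15% | 0.5 | 74.5% | 73.5% | 70.2% |
| 15% | 0.2 | 70.4% | 60.7% | 70.2% |
| 40% | 0.5 | 69.6% | 67.8% | 54.6% |
| 40% | 0.2 | 57.4% | 43.7% | 54.6% |

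Under equal variance the pooled analysis is as good or better in every row. Under additive error, restriction wins only where reliability in the young is 0.2.

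**The case against.** Much of the case on the other side stands.

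- **The scale itself.** A reader might infer that the youngest children cannot use this VAS and that the correlation is therefore diluted. The SAP does not support that. Its appendix is not shown and may hold a form suited to young children. How the scale is administered is commonly left to the protocol, and the plan gives neither reliability nor age mix. Only the possibility of dilution remains.
- **The only severity measure.** A reader might infer this too. The VAS is the only measure of pain intensity named, but PedMIDAS and a headache diary are also recorded, and the plan never says which variable severity is. Neither clearly replaces the VAS: PedMIDAS measures disability and is truncated by the entry criterion, and the diary's content is not described.
- **Restricting the main analysis to older children.** This looks like a remedy for dilution, but the power table shows it can lose more through sample size than it regains. It is a trade-off, not a correction.
- **Stacked assumptions.** The spurious correlation needs age to be related to both score and metabolite. The SAP shows neither, and this is one exploratory correlation among several. The case-control comparison, ROC analysis and logistic regression do not depend on it.

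The last point limits the priority but does not remove the concern. Pooling over 4 to 18 years without an age term leaves the analysis open to this bias even if the appendix holds a well-chosen scale, and the adjusting variable is already recorded.

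**Conclusion.** The concern holds in a limited form. The plan pools severity over cases aged 4-18 with no age term and does not say which variable severity is. Under the assumed shifts (1 SD in VAS, 0.5 SD in metabolite, 15-40% young), a true correlation of 0 appears as about 0.06-0.10, and the false-positive rate at an assumed 100 cases is about 9-18%. With smaller shifts, or if either variable is unrelated to age, the bias shrinks or vanishes. Dilution is possible, but its size cannot be determined from the plan: the illustrations run from about 1% to 33%. The documents establish neither that the VAS is invalid in the youngest nor that older children should form the main analysis.

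**What to change.** In SAP 2.1.4(2), and to match in 1.2.1:

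1. State that severity is the VAS score, and that it is correlated with each metabolite's plasma level.
2. Make the analysis a partial correlation given age, in all cases. If the relation with age is clearly not linear, use age bands or a rank-based version, since a linear age term would then leave some of the bias.
3. Add a sensitivity analysis restricted to older children, with the age limit set and justified before the data are examined. Report it beside the all-ages result, not in its place.

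The cost is a few lines of SAP wording. Age is already collected, the adjustment uses one degree of freedom for a linear term, and no case is dropped from the main analysis.
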